1. SITE INFORMATION							
Site Number	Investigator			Country			
Reporter		Phone Number ()			Fax Number ()		
2. SUBJECT INFORMATION							
Subject ID Number	Age at event onset			Sex  F  M	Race	If applicable, provide End of Study date	
If this is a follow-up to an event reported in the EDC system (eg. Rave), provide the adverse event term: _____ and start date: Day ____ Month ____ Year _____							
3. SERIOUS ADVERSE EVENT							
Provide the date the Investigator became aware of this information: Day ____ Month ____ Year _____. Serious Adverse Event diagnosis or syndrome If diagnosis is unknown, enter signs / symptoms and provide diagnosis, when known, in a follow-up report List one event per line. If event is fatal, enter the cause of death. Entry of "death" is not acceptable, as this is an outcome.							
Serious Adverse Event diagnosis or syndrome If diagnosis is unknown, enter signs / symptoms and provide diagnosis, when known, in a follow-up report List one event per line. If event is fatal, enter the cause of death. Entry of "death" is not acceptable, as this is an outcome.	Date Started	Date Ended	Check only if event occurred before first dose or IP	If event serious? Is the event serious?  Yes  No	Relationship Is there a reasonable possibility that the Event may have been caused by IP (AMG 910) or an Amgen device used to administer the IP?	Outcome of Event  Resolved  Not resolved  Pending  Unknown	Check only if event is related to study procedure  e.g. biopsy
	Day	Month	Year	Day	Month	Year	
Serious Criteria: 01 Fatal 02 Immediately life-threatening		03 Required prolonged hospitalization 04 Persistent or significant disability / incapacity			05 Congenital anomaly / birth defect 06 Other medically important serious event		
4. Was subject hospitalized or was a hospitalization prolonged due to this event?  No  Yes If yes, please complete all of Section 4							
Date Admitted Day Month Year				Date Discharged Day Month Year			
5. Was IP/drug under study administered/taken prior to this event?  No  Yes If yes, please complete all of Section 5							
IP/Amgen Device: AMG 910		Date of Initial Dose Day Month Year	Date of Dose Day Month Year	Prior to, or at time of Event Dose Route Frequency	Action Taken with Product 01 Still being Administered 02 Permanently discontinued 03 Withheld	Lot # and Serial # Lot # _____  Unknown Serial # _____  Unavailable / Unknown	

Figure 11-1. Sample Electronic Serious Adverse Event Contingency Report Form

A Study # 20180292 AMG 910	Electronic Serious Adverse Event Contingency Report Form For Restricted Use								
	Site Number			Subject ID Number					
6. CONCOMITANT MEDICATIONS (eg, chemotherapy) Any Medications?  No  Yes If yes, please complete:									
Medication Name(s)	Start Date Day Month Year	Stop Date Day Month Year	Co-suspect  No  Yes	Continuing  No  Yes	Dose	Route	Freq.	Treatment Med  No  Yes	
7. RELEVANT MEDICAL HISTORY (include dates, allergies and any relevant prior therapy)									
8. RELEVANT LABORATORY VALUES (include baseline values) Any Relevant Laboratory values?  No  Yes If yes, please complete:									
Date Day Month Year	Test								
	Unit								
9. OTHER RELEVANT TESTS (diagnostics and procedures) Any Other Relevant tests?  No  Yes If yes, please complete:									
Date Day Month Year	Additional Tests			Results			Units		

Figure 11-1. Sample Electronic Serious Adverse Event Contingency Report Form

11.5 Appendix 5. Contraceptive Guidance and Collection of Pregnancy and Lactation Information

Study-specific contraception requirements for male and female of childbearing potential are outlined in Section 5.2.

Male and female subjects of childbearing potential must receive pregnancy prevention counseling and be advised of the risk to the fetus if they become pregnant or father a child during treatment and for 75 days for females and 5 months for males after the last dose of protocol-required therapies.

Definition of Females of Childbearing Potential

A female is considered fertile following menarche and until becoming post-menopausal unless permanently sterile. Permanent sterilization methods include hysterectomy, bilateral salpingectomy, and bilateral oophorectomy.

Females in the following categories are not considered female of childbearing potential:

- Premenopausal female with 1 of the following:
 - Documented hysterectomy;
 - Documented bilateral salpingectomy; or
 - Documented bilateral oophorectomy.

Note: Site personnel documentation from the following sources is acceptable:

- 1) review of subject's medical records; 2) subject's medical examination; or
- 3) subject's medical history interview.

- Premenarchal female
- Postmenopausal female
 - A postmenopausal state is defined as no menses for 12 months without an alternative medical cause. A high follicle stimulating hormone (FSH) level in the postmenopausal range may be used to confirm a postmenopausal state in women not using hormonal contraception or hormonal replacement therapy (HRT). However, in the absence of 12 months of amenorrhea, a single FSH measurement is insufficient.
 - Females on HRT and whose menopausal status is in doubt will be required to use 1 of the non-hormonal highly effective contraception methods if they wish to continue their HRT during the study. Otherwise, they must discontinue HRT to allow confirmation of postmenopausal status before study enrollment

Contraception Methods for Female Subjects

Highly Effective Contraceptive Methods

Note: Failure rate of <1% per year when used consistently and correctly.

- Combined (estrogen and progestogen containing) hormonal contraception associated with inhibition of ovulation (oral, intravaginal, or transdermal)
- Progestogen-only hormonal contraception associated with inhibition of ovulation (oral, injectable, implantable)
- Intrauterine device
- Intrauterine hormonal-releasing system
- Bilateral tubal ligation/occlusion
- Vasectomized partner (provided that partner is the sole sexual partner of the female subject of childbearing potential and that the vasectomized partner has received medical assessment of the surgical success)
- Sexual abstinence (defined as refraining from heterosexual intercourse during the entire period of risk associated with the study treatments; the reliability of sexual abstinence must be evaluated in relation to the duration of the trial and the preferred and usual lifestyle of the subject)

Contraception Methods for Male Subjects

- Sexual abstinence (defined as refraining from heterosexual intercourse during the entire period of risk associated with protocol-required therapies; the reliability of sexual abstinence must be evaluated in relation to the duration of the trial and the preferred and usual lifestyle of the subject)
- Use a condom during treatment and for an additional 5 months after the last dose of protocol-required therapies

The female partner should consider using an acceptable method of effective contraception such as: hormonal, IUD, IUS, female barrier method (diaphragm, cap, sponge [a female condom is not an option because there is a risk of tearing when both partners use a condom]).

Note: If the male's sole female partner is of non-childbearing potential or has had a bilateral tubal ligation/occlusion, he is not required to use additional forms of contraception during the study.

Unacceptable Methods of Birth Control for Male and Female Subjects

Birth control methods that are considered unacceptable in clinical trials include:

- Periodic abstinence (calendar, symptothermal, post-ovulation methods)
- Withdrawal (coitus interruptus)
- Spermicides only
- Lactational amenorrhea method

Collection of Pregnancy Information

Female Subjects Who Become Pregnant

- Investigator will collect pregnancy information on any female subject who becomes pregnant while taking protocol-required therapies through an additional 75 days after discontinuation of the study drug.
- Information will be recorded on the Pregnancy Notification Form (see [Figure 11-2](#)). The form must be submitted to Amgen Global Patient Safety within 24 hours of learning of a subject's pregnancy. (Note: Sites are not required to provide any information on the Pregnancy Notification Form that violates the country or regions local privacy laws).
- After obtaining the female subject's signed consent for release of pregnancy and infant health information, the investigator will collect pregnancy and infant health information and complete the pregnancy questionnaire for any female subject who becomes pregnant while taking protocol-required therapies through an additional 75 days after discontinuation of the study drug. This information will be forwarded to Amgen Global Patient Safety. Generally, infant follow-up will be conducted up to 12 months after the birth of the child (if applicable).
- Any termination of pregnancy will be reported to Amgen Global Patient Safety, regardless of fetal status (presence or absence of anomalies) or indication for procedure.
- While pregnancy itself is not considered to be an adverse event or serious adverse event, any pregnancy complication or report of a congenital anomaly or developmental delay, fetal death, or suspected adverse reactions in the neonate will be reported as an adverse event or serious adverse event. Note that an elective termination with no information on a fetal congenital malformation or maternal complication is generally not considered an adverse event, but still must be reported to Amgen as a pregnancy exposure case.
- If the outcome of the pregnancy meets a criterion for immediate classification as a serious adverse event (eg, female subject experiences a spontaneous abortion, stillbirth, or neonatal death or there is a fetal or neonatal congenital anomaly) the investigator will report the event as a serious adverse event.
- Any serious adverse event occurring as a result of a post-study pregnancy which is considered reasonably related to the study treatment by the investigator, will be reported to Amgen Global Patient Safety as described in [Section 11.2](#). While the investigator is not obligated to actively seek this information in former study subjects, he or she may learn of a serious adverse event through spontaneous reporting.
- Any female subject who becomes pregnant while participating will discontinue study treatment (see [Section 7.1](#) for details).

Male Subjects With Partners Who Become Pregnant or Were Pregnant at the Time of Enrollment

- In the event a male subject fathers a child during treatment, and for an additional 5 months after discontinuing protocol-required therapies, the information will be recorded on the Pregnancy Notification Form. The form (see [Figure 11-2](#)) must be submitted to Amgen Global Patient Safety within 24 hours of the site's awareness of the pregnancy. (Note: Sites are not required to provide any information on the Pregnancy Notification Form that violates the country or regions local privacy laws).
- The investigator will attempt to obtain a signed authorization for release of pregnancy and infant health information directly from the pregnant female partner to obtain additional pregnancy information.
- After obtaining the female partner's signed authorization for release of pregnancy and infant health information, the investigator will collect pregnancy outcome and infant health information on the pregnant partner and her baby and complete the pregnancy questionnaires. This information will be forwarded to Amgen Global Patient Safety.
- Generally, infant follow-up will be conducted up to 12 months after the birth of the child (if applicable).
- Any termination of the pregnancy will be reported to Amgen Global Patient Safety regardless of fetal status (presence or absence of anomalies) or indication for procedure.

Collection of Lactation Information

- Investigator will collect lactation information on any female subject who breastfeeds while taking protocol-required therapies through an additional 75 days after discontinuation of the study drug.
- Information will be recorded on the Lactation Notification Form (see below) and submitted to Amgen Global Patient Safety within 24 hours of the investigator's knowledge of event.
- Study treatment will be discontinued if female subject breastfeeds during the study as described in exclusion criterion 216.
- With the female subjects signed authorization for release of mother and infant health information, the investigator will collect mother and infant health information and complete the lactation questionnaire on any female subject who breastfeeds while taking protocol-required therapies through an additional 75 days after discontinuing protocol-required therapies.

Figure 11-2. Pregnancy and Lactation Notification Forms

Amgen Proprietary- Confidential

AMGEN® Pregnancy Notification Form

Report to Amgen at: USTO [contact], Non-US [contact] or email (worldwide): [contact]

1. Case Administrative Information

Protocol/Study Number: 20180292

Study Design: Interventional Observational (If Observational: Prospective Retrospective)

2. Contact Information

Investigator Name _____ Site # _____

Phone (____) _____ Fax (____) _____ Email _____

Institution _____

Address _____

3. Subject Information

Subject ID # _____ Subject Gender: Female Male Subject age (at onset): _____ (in years)

4. Amgen Product Exposure

Amgen Product	Dose at time of conception	Frequency	Route	Start Date
AMG 910				mm ____/dd ____/yyyy ____

Was the Amgen product (or study drug) discontinued? Yes No

If yes, provide product (or study drug) stop date: mm ____/dd ____/yyyy ____

Did the subject withdraw from the study? Yes No

5. Pregnancy Information

Pregnant female's last menstrual period (LMP) mm ____/dd ____/yyyy ____ Unknown N/A

Estimated date of delivery mm ____/dd ____/yyyy ____
If N/A, date of termination (actual or planned) mm ____/dd ____/yyyy ____

Has the pregnant female already delivered? Yes No Unknown N/A

If yes, provide date of delivery: mm ____/dd ____/yyyy ____

Was the infant healthy? Yes No Unknown N/A

If any Adverse Event was experienced by the infant, provide brief details: _____

Form Completed by:

Print Name: _____ Title: _____

Signature: _____ Date: _____

Figure 11-2. Pregnancy and Lactation Notification Forms

Amgen Proprietary- Confidential

AMGEN® Lactation Notification Form

Report to Amgen at: USTO [contact], Non-US [contact] or email (worldwide): [contact]

1. Case Administrative Information

Protocol/Study Number: 20180292

Study Design: Interventional Observational (If Observational: Prospective Retrospective)

2. Contact Information

Investigator Name _____ Site # _____

Phone (____) _____ Fax (____) _____ Email _____

Institution _____

Address _____

3. Subject Information

Subject ID # _____ Subject age (at onset): _____ (in years)

4. Amgen Product Exposure

Amgen Product	Dose at time of breast feeding	Frequency	Route	Start Date
AMG 910				mm ____/dd ____/yyyy ____

Was the Amgen product (or study drug) discontinued? Yes No

If yes, provide product (or study drug) stop date: mm ____/dd ____/yyyy ____

Did the subject withdraw from the study? Yes No

5. Breast Feeding Information

Did the mother breastfeed or provide the infant with pumped breast milk while actively taking an Amgen product? Yes No

If No, provide stop date: mm ____/dd ____/yyyy ____

Infant date of birth: mm ____/dd ____/yyyy ____

Infant gender: Female Male

Is the infant healthy? Yes No Unknown N/A

If any Adverse Event was experienced by the mother or the infant, provide brief details: _____

Form Completed by:

Print Name: _____ Title: _____

Signature: _____ Date: _____

11.6 Appendix 6. Sample Storage and Destruction

Any blood, tumor, biomarker, or pharmacokinetic (PK) sample collected according to the Schedule of Activities (Table 1-1) can be analyzed for any of the tests outlined in the protocol and for any tests necessary to minimize risks to study subjects. This includes testing to ensure analytical methods produce reliable and valid data throughout the course of the study. This can also include, but is not limited to, investigation of unexpected results, incurred sample reanalysis, and analyses for method transfer and comparability.

All samples and associated results will be coded prior to being shipped from the site for analysis or storage. Samples will be tracked using a unique identifier that is assigned to the samples for the study. Results are stored in a secure database to ensure confidentiality.

[REDACTED]

Results from this analysis are to be documented and maintained, but are not necessarily reported as part of this study. Samples can be retained for up to 20 years.

Since the evaluations are not expected to benefit the subject directly or to alter the treatment course, the results of pharmacogenetic, biomarker development or other exploratory studies are not placed in the subject's medical record and are not to be made available to the subject, members of the family, the personal physician, or other third parties, except as specified in the informed consent.

The subject retains the right to request that the sample material be destroyed by contacting the investigator. Following the request from the subject, the investigator is to provide the sponsor with the required study and subject number so that any remaining sample types (eg, blood, tumor) samples and any other components from the cells can be located and destroyed. Samples will be destroyed once all protocol-defined procedures are completed. However, information collected from samples prior to the request for destruction, will be retained by Amgen.

The sponsor is the exclusive owner of any data, discoveries, or derivative materials from the sample materials and is responsible for the destruction of the sample(s) at the request of the subject through the investigator, at the end of the storage period, or as appropriate (eg, the scientific rationale for experimentation with a certain sample type no

longer justifies keeping the sample). If a commercial product is developed from this research project, the sponsor owns the commercial product. The subject has no commercial rights to such product and has no commercial rights to the data, information, discoveries, or derivative materials gained or produced from the sample. See Section [11.3](#) for subject confidentiality.

11.7 Appendix 7. Hepatotoxicity Stopping Rules: Suggested Actions and Follow-up Assessments and Study Treatment Rechallenge Guidelines

Subjects with abnormal hepatic laboratory values (ie, alkaline phosphatase [ALP], aspartate aminotransferase [AST], alanine aminotransferase [ALT], total bilirubin [TBL]) and/or international normalized ratio (INR) and/or signs/symptoms of hepatitis (as described below) may meet the criteria for withholding or permanent discontinuation of Amgen investigational product or other protocol-required therapies, as specified in the *Guidance for Industry Drug-Induced Liver Injury: Premarketing Clinical Evaluation, July 2009*.

Criteria for Withholding and/or Permanent Discontinuation of Amgen Investigational Product and Other Protocol-required Therapies Due to Potential Hepatotoxicity

The following stopping and/or withholding rules apply to subjects for whom another cause of their changes in liver biomarkers (TBL, INR and transaminases) has not been identified.

Important alternative causes for elevated AST/ALT and/or TBL values include, but are not limited to:

- Hepatobiliary tract disease
- Viral hepatitis (eg, hepatitis A/B/C/D/E, Epstein-Barr Virus, cytomegalovirus, herpes simplex virus, varicella, toxoplasmosis, and parvovirus)
- Right sided heart failure, hypotension or any cause of hypoxia to the liver causing ischemia
- Exposure to hepatotoxic agents/drugs or hepatotoxins, including herbal and dietary supplements, plants and mushrooms
- Heritable disorders causing impaired glucuronidation (eg, Gilbert's syndrome, Crigler-Najjar syndrome) and drugs that inhibit bilirubin glucuronidation (eg, indinavir, atazanavir)
- Alpha-one antitrypsin deficiency
- Alcoholic hepatitis
- Autoimmune hepatitis
- Wilson's disease and hemochromatosis
- Nonalcoholic fatty liver disease including steatohepatitis
- Non-hepatic causes (eg, rhabdomylosis, hemolysis)

If investigational product(s) is/are withheld, the subject is to be followed for possible drug induced liver injury (DILI) according to recommendations in the last section of this appendix.

Rechallenge may be considered if an alternative cause for impaired liver tests (ALT, AST, ALP) and/or elevated TBL, is discovered and the laboratory abnormalities resolve to normal or baseline (see next section in this appendix).

Table 11-3. Conditions for Withholding and/or Permanent Discontinuation of Amgen Investigational Product and Other Protocol-required Therapies Due to Potential Hepatotoxicity

Analyte	Temporary Withholding	Permanent Discontinuation
TBL	> 3x ULN at any time	> 2x ULN OR
INR	--	> 1.5x (for subjects not on anticoagulation therapy) OR
AST/ALT	> 8x ULN at any time > 5x ULN but < 8x ULN for \geq 2 weeks > 5x ULN but < 8x ULN and unable to adhere to enhanced monitoring schedule > 3x ULN with clinical signs or symptoms that are consistent with hepatitis (such as right upper quadrant pain/tenderness, fever, nausea, vomiting, and jaundice)	In the presence of no important alternative causes for elevated AST/ALT and/or TBL values > 3x ULN (when baseline was < ULN)
ALP	> 8x ULN at any time	--

ALP = alkaline phosphatase; ALT = alanine aminotransferase; AST = aspartate aminotransferase; INR = international normalized ratio; TBL = total bilirubin; ULN = upper limit of normal

Criteria for Rechallenge of Amgen Investigational Product and Other Protocol-required Therapies After Potential Hepatotoxicity

The decision to rechallenge the subject is to be discussed and agreed upon unanimously by the subject, investigator, and Amgen.

If signs or symptoms recur with rechallenge, then AMG 910 is to be permanently discontinued. Subjects who clearly meet the criteria for permanent discontinuation (as described in [Table 11-3](#)) are never to be rechallenged.

Drug-induced Liver Injury Reporting and Additional Assessments

Reporting

To facilitate appropriate monitoring for signals of DILI, cases of concurrent AST or ALT and TBL and/or INR elevation, according to the criteria specified in the above, require the following:

- The event is to be reported to Amgen as a serious adverse event within 24 hours of discovery or notification of the event (ie, before additional etiologic investigations have been concluded)
- The appropriate Case Report Form (CRF) (eg, Events CRF) that captures information necessary to facilitate the evaluation of treatment-emergent liver abnormalities is to be completed and sent to Amgen

Other events of hepatotoxicity and potential DILI are to be reported as serious adverse events if they meet the criteria for a serious adverse event defined in Section 11.4.

Additional Clinical Assessments and Observation

All subjects in whom investigational product(s) or protocol-required therapies is/are withheld (either permanently or conditionally) due to potential DILI as specified in [Table 11-3](#) or who experience AST or ALT elevations $> 3 \times$ upper limit of normal (ULN) or 2-fold increases above baseline values for subjects with elevated values before drug are to undergo a period of “close observation” until abnormalities return to normal or to the subject’s baseline levels.

Assessments that are to be performed during this period include:

- Repeat AST, ALT, ALP, bilirubin (BIL) (total and direct), and INR within 24 hours
- In cases of TBL $> 2 \times$ ULN or INR > 1.5 , retesting of liver tests, BIL (total and direct), and INR is to be performed every 24 hours until laboratory abnormalities improve

Testing frequency of the above laboratory tests may decrease if the abnormalities stabilize or the investigational product(s) or protocol-required therapies has/have been discontinued AND the subject is asymptomatic.

Initiate investigation of alternative causes for elevated AST or ALT and/or elevated TBL.

The following are to be considered depending on the clinical situation:

- Complete blood count with differential to assess for eosinophilia
- Serum total immunoglobulin (Ig)G, anti-nuclear antibody anti-smooth muscle antibody, and liver kidney microsomal antibody-1 to assess for autoimmune hepatitis
- Serum acetaminophen (paracetamol) levels

- A more detailed history of:
 - Prior and/or concurrent diseases or illness
 - Exposure to environmental and/or industrial chemical agents
 - Symptoms (if applicable) including right upper quadrant pain, hypersensitivity-type reactions, fatigue, nausea, vomiting and fever
 - Prior and/or concurrent use of alcohol, recreational drugs and special diets
 - Concomitant use of medications (including non-prescription medicines and herbal and dietary supplements), plants, and mushrooms
- Viral serologies
- Creatine phosphokinase, haptoglobin, lactate dehydrogenase and peripheral blood smear
- Appropriate liver imaging if clinically indicated
- Appropriate blood sampling for pharmacokinetic analysis if this has not already been collected
- Hepatology consult (liver biopsy may be considered in consultation with a hepatologist)

Follow the subject and the laboratory tests (ALT, AST, TBL, INR) until all laboratory abnormalities return to baseline or normal or considered stable by the investigator. The "close observation period" is to continue for a minimum of 4 weeks after discontinuation of all investigational product(s) and protocol-required therapies.

The potential DILI event and additional information such as medical history, concomitant medications and laboratory results must be captured in the corresponding CRFs.

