6.2.1.3 Dose-limiting Toxicity

The adverse event grading scale to be used for this study will be the CTCAE version 5.0 and is described in Section 11.4, with the exception of CRS, which will be graded using

the criteria referenced in the publication by Lee et al (2014) (see Section 11.13) and TLS, which will be graded according to the Cairo Bishop criteria referenced in the publication by Coiffier et al (2008) (see Section 11.14).

Dose-limiting toxicities are defined as any adverse events at least possibly related to AMG 910 with an onset within the first 28 days following first dose for single-subject cohorts and within the safety observation period for multiple-subject cohorts as defined in Section 6.2.1.1.2 with any of the following criteria:

- grade 2 gastric perforation or fistula
- grade ≥ 3 non-hematologic adverse events including laboratory abnormalities with the exceptions as stated below:
 - grade 3 fever (not associated with any other CRS/**infusion-related reaction** symptoms) that does improve to grade ≤ 1 within 72 hours
 - grade 3 nausea, vomiting, or diarrhea that does improve to grade ≤ 1 or baseline within 72 hours with optimal medical support.
 - grade 3 asymptomatic liver enzyme elevations including AST, ALT, GGT with AST improving to grade ≤ 2 within 72 hours and ALT and GGT, which have long half-lives, improving to grade ≤ 2 within 7 days except those meeting Hy's Law
- re-challenge with AMG 910 after treatment interruption due to any stomach toxicity results in at least same stomach toxicity and is of CTCAE grade ≥ 3 or grade 2 and ongoing for more than 3 days despite optimal supportive treatment
- grade 4 thrombocytopenia or grade 3 thrombocytopenia with bleeding
- grade 4 neutropenia lasting longer than 28 days
- febrile neutropenia of any grade
- anemia requiring transfusion per local or international guidelines in the absence of bleeding
- grade 5 toxicity (eg, death not due to disease progression)
- any other toxicity related to AMG 910 considered significant enough to be qualified as DLT in the opinion of the investigator, and confirmed by the DLRT, will be reported as DLT

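### As printed, Table 11-3 joins its permanent liver-stopping criteria with OR, so unexplained rises too mild for any temporary hold end treatment for good, and the table's tiers contradict each other

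*Protocol*

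**What the plan says.** Protocol Section 11.7 (Appendix 7) limits the stopping and withholding rules to a defined group: they "apply to subjects for whom another cause of their changes in liver biomarkers (TBL, INR and transaminases) has not been identified". Table 11-3 then has two columns.

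- **Permanent discontinuation.** TBL above 2x ULN, followed by OR. INR: "> 1.5x (for subjects not on anticoagulation therapy) OR". AST/ALT: "In the presence of no important alternative causes for elevated AST/ALT and/or TBL values > 3x ULN (when baseline was < ULN". ALP has no entry.
- **Temporary withholding, six conditions.** TBL above 3x ULN; AST/ALT above 8x; AST/ALT between 5x and 8x for two weeks or more; AST/ALT between 5x and 8x when the subject cannot keep to closer monitoring; AST/ALT "> 3x ULN with clinical signs or symptoms that are consistent with hepatitis (such as right upper quadrant pain/tenderness, fever, nausea, vomiting, and jaundice"; ALP above 8x. INR has no hold.

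On coming back to treatment, the text before the table says: "Rechallenge may be considered if an alternative cause for impaired liver tests" is discovered and the values resolve. The text after it says that subjects who clearly meet the permanent criteria "are never to be rechallenged". The reporting paragraph that follows refers to "cases of concurrent AST or ALT and TBL and/or INR elevation, according to the criteria specified in the above".

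**The concern.** With OR between all three rows, each analyte alone is enough for a permanent stop. The permanent thresholds (TBL 2x, AST/ALT 3x) are at or below the corresponding hold thresholds (TBL 3x; AST/ALT 3x with symptoms, 5x, 8x). The milder action would then need an equal or worse laboratory value, which makes sense only if the permanent criterion is a combination of findings.

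What is at stake is treatment for subjects whose rise is unexplained but modest. An isolated TBL between 2x and 3x, an isolated INR above 1.5x, or an asymptomatic AST/ALT between 3x and 5x meets no hold. Read literally, each is a permanent stop with rechallenge barred.

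**Working it through.** The plan states no figure on this point, so there is none to reproduce. The check is an enumeration of the rule.

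**Inputs** (all from Table 11-3 and its scope sentence): no other cause identified; baseline AST/ALT below ULN unless stated; not on anticoagulation where INR is used.

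- Rule as printed: permanent if TBL > 2 OR INR > 1.5 OR AST/ALT > 3 (multiples of ULN, except that INR is as the table gives it).
- Comparison rule: permanent if (TBL > 2 OR INR > 1.5) AND AST/ALT > 3.

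**Step 1: does meeting a hold already meet the permanent rule?**

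| Hold | As printed | With AND |
|---|---|---|
| TBL > 3 | yes (3 > 2) | no |
| AST/ALT > 8 | yes (8 > 3) | no |
| AST/ALT 5-8, two weeks or more | yes (5 > 3) | no |
| AST/ALT 5-8, cannot be monitored | yes (5 > 3) | no |
| AST/ALT > 3 with symptoms | yes (same threshold) | no |
| ALP > 8 | no | no |
| **Total** | **5 of 6** | **0 of 6** |

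**Step 2: grid of 3 TBL bands (up to 2, >2-3, >3) by 4 AST/ALT bands (up to 3, >3-5, >5-8, >8) = 12 cells.** INR is at most 1.5x, ALP at most 8x, no symptoms, and any 5-8x rise is monitored and under two weeks old.

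- As printed, only the cell with TBL up to 2 and AST/ALT up to 3 escapes: 12 - 1 = 11 permanent, 0 hold only, 1 no action.
- With AND, permanent needs TBL > 2 (2 bands) and AST/ALT > 3 (3 bands): 2 x 3 = 6. Hold only: TBL > 3 with AST/ALT up to 3, and AST/ALT > 8 with TBL up to 2, so 2. No action: 12 - 6 - 2 = 4.

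**Step 3: cells that meet no hold.** These have TBL up to 3 (2 bands) and AST/ALT up to 8 (3 bands): 2 x 3 = 6. As printed, 6 - 1 = 5 are permanent stops. With AND, only TBL >2-3 with AST/ALT >3-5 or >5-8 are permanent, so 2. With AND no rise in a single analyte ends treatment.

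**Step 4: variations.**

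- With hepatitis symptoms, no action / hold only / permanent is 1 / 0 / 11 as printed and 2 / 4 / 6 with AND.
- With INR above 1.5x and no anticoagulation, 12 of 12 cells are permanent as printed. With AND, the 3 cells with AST/ALT up to 3 drop out, leaving 9.
- With baseline AST/ALT at or above ULN, the AST/ALT permanent row does not apply. As printed, only TBL > 2 triggers: 2 x 4 = 8 of 12 cells, and 1 of 6 holds (TBL) is already permanent. With AND, 0 of 12 cells are permanent. Section 5.1, criterion 111, admits such subjects (AST/ALT below 3x ULN, or below 5x with liver involvement).

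**Step 5: the text against itself.** The hold for 5-8x in a subject who cannot be monitored closely presupposes that one who can be monitored keeps dosing. As printed, that subject has already stopped permanently. The reporting paragraph describes AST or ALT elevation together with TBL and/or INR elevation, and attributes that to the criteria above it. This is the AND structure.

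**The case against.** **A hold can still act, and hold and stop partly converge.** A reader might infer from 5 of 6 that these holds never operate. The documents do not support that. A hold can begin while the search for another cause is under way, and the AST/ALT permanent cell depends on that search finding none. The rechallenge sentence follows directly from the sentence on withheld product, so it also ties return after a temporary hold to finding an alternative cause. If none is found, a held subject has no clearly stated route back either. If one is found, the scope sentence takes the subject out of the permanent rule. This stands, and it reduces the practical difference for subjects who already meet a hold. It does not help those whose rise meets no hold.

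**The table was machine-read.** The AST/ALT permanent cell runs a clause about causes straight into the threshold, which suggests a merged or flattened layout. Both ORs are legible in the text available, but the layout needs confirming. This also stands.

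**The intent can be read from the text.** The reporting paragraph points to a combination, the appendix title speaks of suggested actions and guidelines, and the bar on rechallenge covers only those who clearly meet the criteria. This makes misapplication less certain. However, Section 6.2.3 and the last row of Table 6-3 send sites to this appendix for the stopping rules, and the table contains no AND to apply.

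**AND alone is incomplete.** It removes every permanent criterion for subjects with baseline AST/ALT at or above ULN. This is correct, and the fix must cover it.

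**Conclusion.** The point holds for the text as printed. With no other cause identified and baseline AST/ALT below ULN, 5 of 6 hold thresholds sit at or above a permanent threshold, and 5 of the 6 grid cells that meet no hold are permanent stops, against 2 with AND. The main consequence is for these milder rises: isolated TBL >2-3x, isolated INR above 1.5x, asymptomatic AST/ALT >3-5x, and monitored 5-8x for under two weeks.

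The conclusion assumes that the source PDF also prints OR. The INR trigger applies only without anticoagulation. That AND was meant is an inference from the tiers and the reporting paragraph. Grid cells are combinations of rules, not risks; the documents give no event frequency and none is claimed. The error is conservative and narrow in scope, so it should be fixed but is not critical.

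Two further readings are tempting and are not used as support.

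- A reader might infer a contradiction with Section 6.2.1.3, which exempts some transient enzyme rises from being DLTs. That rule counts toxicities for dose escalation, whereas Table 11-3 governs one subject's treatment, so they may differ.
- A reader might infer a conflict with the CRS restart rows or with Section 6.2.2.3.2, which lists grade 3 transaminitis among events that should not interrupt the extended infusion. That would depend on CTCAE cut-offs the protocol does not print and on whether CRS counts as another cause, which it does not say.

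**What to change.** 1. Confirm the connectors in the source PDF.
2. If they read OR, change the one before the AST/ALT row to AND. Permanent discontinuation then requires (TBL above 2x ULN, or INR above 1.5x if not on anticoagulation) AND AST/ALT above 3x ULN with baseline below ULN, and no important alternative cause.
3. In the same edit, add a permanent AST/ALT criterion for subjects with baseline AST/ALT at or above ULN, with the same TBL/INR condition. The clinical team should choose the threshold.
4. Keep all six temporary holds in force.

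The cost is one connector, one added table entry and a clinical decision on one threshold. No subjects or procedures are added. SAP Section 7.1 records that the study was terminated early, so for this trial it is also worth checking any hepatic discontinuations made under the table as printed.
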